### **TB Test**

For regions that require both PPD and QuantiFERON-TB Gold testing, both will be performed. A positive TB test is defined by local guidelines (for example, in some countries, both PPD and QuantiFERON-TB Gold are performed, and if either one is positive, the TB test is considered positive).

In the absence of local guidelines defining a positive result when both PPD and QuantiFERON-TB Gold tests are performed, the TB test is considered positive if either one is positive.

If a site has the capacity to perform both PPD and QuantiFERON-TB Gold tests, and local guidelines require only one test to be performed, then the QuantiFERON-TB Gold is the preferred test. If only a PPD is placed at screening, then the PPD will be the reference TB test to be used for the remainder of the program for that subject. Similarly, if a subject enters the study with a QuantiFERON-TB Gold test alone or other IGRA (negative result), then any future TB test performed should be a QuantiFERON-TB Gold test.

If the QuantiFERON-TB Gold Test is NOT possible (or if both the QuantiFERON-TB Gold Test and the PPD are required per local guidelines): the PPD will be performed according to standard clinical practice. The TB Skin Test should be read by a licensed healthcare professional between 48 and 72 hours after administration. A subject who does not return within 72 hours will need to be rescheduled for another skin test. The reaction will be measured in millimeters (mm) of induration and induration  $\geq 5$  mm is considered a positive reaction. The absence of induration will be recorded as "0 mm" not "negative." Subjects who have had a prior positive PPD test or an ulcerating reaction to the TB Skin Test in the past should not be re-exposed and the TB Skin Test should be considered positive.

Subjects with a negative TB test and chest x-ray not suggestive of active TB or prior TB exposure may be enrolled.

If the QuantiFERON-TB Gold test is indeterminate, the site should repeat the test with another blood sample and/or perform a PPD test. If the second QuantiFERON TB Gold test is also indeterminate or positive, the subject is considered to be positive for the purpose of the study. If the second QuantiFERON-TB Gold test is negative, the subject is considered to be negative.

In cases where the Screening QuantiFERON-TB Gold test by the central laboratory is positive and the investigator considers the subject at low risk for TB (i.e., no risk factors identified using the TB risk assessment form) and has no clinical suspicion of TB, the investigator may perform a repeat QuantiFERON-TB Gold test (or IGRA equivalent) at the local laboratory or through the central laboratory (if not locally available) to confirm the positive test result. If the repeat testing result is negative, the investigator may consider the subject to be negative based on his/her clinical judgment. If the repeat testing result is positive or indeterminate, the subject is considered to be positive.

Subjects with a positive TB test must be assessed for evidence of active TB versus latent TB, including signs and symptoms and chest x-ray. Subjects with no signs or symptoms and a chest x-ray not suggestive of active TB may be enrolled after initiation of TB prophylaxis (see below). Subjects with evidence of active TB must not be enrolled.

Subjects with history of active TB may be enrolled if it has been adequately treated with no evidence of current active TB; subjects with inadequate documentation of treatment should be cleared by a TB specialist prior to enrollment.

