### **TB Prophylaxis**

At screening, if the subject has evidence of latent TB infection (no symptoms, positive TB test and the subject has a chest x-ray not suggestive of active TB), prophylactic treatment must be initiated at least 2 weeks prior to administration of study drug (or per local guidelines, whichever is longer). At least 6 months of prophylaxis needs to be completed; however, the full course of prophylaxis does not need to be completed prior to the first dose of study drug. If the investigator deems that it is necessary, consultation with a TB expert could be considered.

In case of a subject at low risk for TB (i.e., no risk factors identified using the TB risk assessment form), no clinical suspicion of TB, who had a negative confirmatory repeat QuantiFERON-TB Gold test result available after initiation of isoniazid, then TB prophylaxis can be stopped.

Note: Rifampicin or rifapentine are not allowed for TB prophylaxis.

Subjects with a prior history of latent TB that have documented completion of a full course of anti-TB therapy will be allowed to enter the study provided nothing has changed in the subject's medical history to warrant repeat treatment.

For subjects with completion of a full course of anti-TB therapy but insufficient documentation the investigator should consult with the AbbVie TA MD.

Newly initiated prophylactic treatment should be captured in the eCRF and in the source documents. Prior therapy should be captured in the eCRF.

During the study, subjects with new evidence of latent TB should initiate prophylactic treatment immediately per local guidelines and complete at least 6 months of prophylaxis. Study drug(s) should not be withheld and isoniazid should be initiated and 2 to 4 weeks later (per local guidelines), subject should be re-evaluated (unscheduled visit) for signs and symptoms of isoniazid toxicity.

If the subject is experiencing signs or symptoms suspicious for active TB or something has changed in the subject's medical history to warrant a repeat test, the case (including the TB test results) must be discussed with the AbbVie TA MD.

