- i. PPD skin test is to be read 48 to 72 hours after placement. Subjects with negative QuantiFERON TB Gold test and/or PPD test within 90 days of Screening will not require a repeat test (documentation must be available). In case of positive PPD/positive or repeat indeterminate IGRA testing, in the absence of active TB, the subject may participate in the study after initiation of latent TB treatment (regimen according to local practice/guidelines).
- j. Chest x-ray includes posterior-anterior view and lateral view. Subjects can have a chest x-ray anytime during the study as warranted based on the opinion of the investigator. In Japan and China, a CT scan of the chest may be performed in lieu of a chest x-ray, at the investigator's discretion.
- k. FSH should be tested at Screening if the female subject is  $\leq$  55 years of age AND has had no menses  $\geq$  12 months AND has no history of permanent surgical sterilization (Refer to Section 5.2.4).
- l. Subjects will be tested for the presence of HBV and HCV at Screening. A positive result for HBs Ag or hepatitis C (HCV RNA detectable in any subject with anti-HCV Ab) will be exclusionary. For subjects who are negative for both HBs Ag and HBs Ab but are positive for HBc Ab, HBV DNA PCR will be performed and any result that meets or exceeds detection sensitivity will be exclusionary. HIV testing will be performed at the central laboratory, unless prohibited by local regulations. The central lab will report the HIV test results directly to the sites. AbbVie will not receive results from the HIV testing and not be made aware of any positive result.

- m. For Japan or countries who mandate periodic screening for HBV: subjects with positive HBs Ab and/or positive HBc Ab and a negative HBV DNA PCR test result at Screening should have HBV DNA PCR test performed at 12 and 24 weeks; in cases where recurrence of HBV DNA is observed, the subject should be discontinued from the study. This measure is not necessary in patients with history of HBV vaccination and positive HBs Ab result.
- n. Laboratory tests performed during the Screening Period can be repeated in case the abnormalities are considered to be transient by the investigator.

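### After an indeterminate QuantiFERON, a negative repeat with a positive PPD is classified TB negative by one protocol rule and handled as positive by two others

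*Protocol*

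**What the plan says.** Four pieces of protocol text bear on the point. Three classify or handle the TB test result, and the fourth sets the consequence.

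- **Indeterminate-result paragraph** (Section 5.3.1.1, TB Test). After an indeterminate QuantiFERON, "the site should repeat the test with another blood sample and/or perform a PPD test". The paragraph then sorts subjects on the second QuantiFERON only. A positive or again indeterminate result counts as positive. For the remaining result it says: "If the second QuantiFERON-TB Gold test is negative, the subject is considered to be negative". The PPD that it has just permitted plays no part in the classification.
- **Either-positive sentence** (same text, earlier). It opens with the condition "In the absence of local guidelines defining a positive result" and continues: "when both PPD and QuantiFERON-TB Gold tests are performed, the TB test is considered positive if either one is positive". Further on, the same text sets the PPD cut-off for a positive reaction at 5 mm of induration or more.
- **Appendix C, footnote i.** "In case of positive PPD/positive or repeat indeterminate IGRA testing, in the absence of active TB, the subject may participate in the study", but only after latent TB treatment has been started. A positive PPD is listed there in its own right.
- **TB Prophylaxis** (Section 5.3.1.1). For a subject with a positive test and no evidence of active disease, "prophylactic treatment must be initiated at least 2 weeks prior to administration of study drug", or for longer if local guidelines require it. At least 6 months must be completed in total. A subject with a negative test and a chest x-ray showing no sign of active TB or earlier exposure may simply be enrolled.

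**The concern.** The indeterminate-result paragraph expressly allows a PPD alongside the repeat QuantiFERON but does not say what the PPD result is for. When the two disagree, a site can follow one sentence and enrol the subject as TB negative with no prophylaxis. It can equally follow another and hold back the first dose until prophylaxis has run for at least 2 weeks. Both sites would be following written protocol text.

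What is at stake is consistent safety handling. These subjects are about to receive a JAK inhibitor, and some will also be on corticosteroids. The protocol lists active TB as an adverse event of special interest and requires study drug to be stopped if it develops. With about 400 sites planned, it cannot be assumed that all will resolve the ambiguity in the same way.

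**Working it through.** The protocol gives no figure on this point, so the check is an enumeration. The first QuantiFERON is fixed as indeterminate. The repeat QuantiFERON has 4 states (negative, positive, indeterminate, not done) and the PPD has 3 (positive, negative, not done). That makes 4 × 3 = 12 combinations. Removing the one with no follow-up test leaves 11.

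Three rules were applied to each combination:
- A: the indeterminate-result paragraph
- B: the either-positive sentence, which needs both tests done and no local definition of the combined result
- C: Appendix C footnote i

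| Repeat QuantiFERON | PPD | Rule A | Rule B | Rule C | Result |
|---|---|---|---|---|---|
| Positive | any of 3 | positive | positive if PPD done | handled as positive | 3 consistent |
| Indeterminate | any of 3 | positive | positive if PPD positive; otherwise adds nothing contrary | handled as positive | 3 consistent |
| Negative | positive | **negative** | **positive** | **handled as positive** | **1 conflict** |
| Negative | negative | negative | no positive result | not triggered | 1 consistent |
| Negative | not done | negative | not applicable | not triggered | 1 consistent |
| Not done | positive | silent | not applicable | handled as positive | 1 covered |
| Not done | negative | silent | not applicable | not triggered | 1 without an explicit rule |

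The rows add up: 3 + 3 + 1 + 1 + 1 + 1 + 1 = 11. Nine combinations have one outcome, one has two opposite outcomes, and one has no explicit outcome. These are counts of combinations, not of subjects, and say nothing about frequency.

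For the conflicting row, the consequences under the protocol's own text are:
- Under A the subject is negative and, given a suitable chest x-ray, may be enrolled with no prophylaxis.
- Under B the subject is positive. Without active TB, prophylaxis must begin at least 2 weeks before study drug.
- Under C the subject may participate only once latent TB treatment has started.

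Nothing in the TB sections of 5.3.1.1 or in Appendix C says which rule yields.

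**The case against.** The case on the other side has several parts.

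*The either-positive sentence has a narrower home.* It follows a sentence about regions that require both tests and is a fallback for when local guidelines are silent. It could therefore be read as the definition for those regions only, with the later and more specific indeterminate-result paragraph prevailing. The condition on local guidelines stands and limits the point. However, the sentence is worded for any case where both tests are performed, and no text gives the specific rule priority. Footnote i would still disagree.

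*Footnote i is a summary.* Section 5.3.1.1 is where procedures are discussed in detail, and the footnote never says the subject is considered positive. That is true. It nevertheless gives a positive PPD the consequence of a positive test, and it makes no exception for a negative repeat QuantiFERON.

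*Doing both tests is unusual.* Elsewhere in Section 5.3.1.1 the PPD is reserved for when a QuantiFERON is not possible or both tests are required locally. This supports a small number of affected subjects but does not remove the permission to do both.

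*The investigator decides.* The protocol makes the investigator responsible for determining TB status in context. This softens the problem, but the disputed sentence is written as a classification, not as a matter of judgement.

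A reader might also infer three stronger claims, which the documents do not support:
- **The same conflict where a positive QuantiFERON is retested.** That text is permissive, is limited to low-risk subjects without clinical suspicion, and relies on clinical judgement. It is silent on a PPD and does not contradict one.
- **Subjects enrolled in breach of entry criteria.** Latent TB is not itself exclusionary, because enrolment is allowed once prophylaxis has begun. Calling such subjects entry-criteria deviations would be speculation.
- **No outcome at all when only a PPD follows.** The 5 mm cut-off and footnote i cover a positive PPD. Only the negative PPD lacks an explicit rule.

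**Conclusion.** The contradiction is real but confined to one combination: first QuantiFERON indeterminate, repeat QuantiFERON negative, PPD positive. For that combination the indeterminate-result paragraph gives a negative classification, while the either-positive sentence and footnote i lead to handling as positive. The disagreement with the either-positive sentence arises only where no local guideline defines the combined result. Beside it is one gap: a negative PPD used as the only follow-up to an indeterminate QuantiFERON.

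The conclusion rests on reading the permission to do both follow-up tests literally and on the absence of any stated precedence. The documents give no frequency for indeterminate or discordant results. The number of subjects is probably small, but for each one the difference is between no prophylaxis and prophylaxis started before the first dose. No endpoint, sample size, power or type I error figure is affected. This is an inconsistency of wording with a safety consequence, and it should be corrected. The documents do not settle which classification is right, and none is proposed here.

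**What to change.** Reconcile the indeterminate-result paragraph and the either-positive sentence of the TB Test text with Appendix C footnote i, so that a negative repeat QuantiFERON with a positive PPD has a single stated outcome. State also what follows when only a PPD is done after an indeterminate QuantiFERON, including when that PPD is negative. A short table of repeat QuantiFERON result against PPD result, cross-referenced from footnote i, would do this and could note where a local definition takes over. The sponsor's medical team must choose the outcomes.

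The cost is protocol wording, by administrative letter or in the next amendment, and a notice to sites. No test is added and the statistical analysis plan does not change.

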### **TB Prophylaxis**

At screening, if the subject has evidence of latent TB infection (no symptoms, positive TB test and the subject has a chest x-ray not suggestive of active TB), prophylactic treatment must be initiated at least 2 weeks prior to administration of study drug (or per local guidelines, whichever is longer). At least 6 months of prophylaxis needs to be completed; however, the full course of prophylaxis does not need to be completed prior to the first dose of study drug. If the investigator deems that it is necessary, consultation with a TB expert could be considered.

In case of a subject at low risk for TB (i.e., no risk factors identified using the TB risk assessment form), no clinical suspicion of TB, who had a negative confirmatory repeat QuantiFERON-TB Gold test result available after initiation of isoniazid, then TB prophylaxis can be stopped.

Note: Rifampicin or rifapentine are not allowed for TB prophylaxis.

Subjects with a prior history of latent TB that have documented completion of a full course of anti-TB therapy will be allowed to enter the study provided nothing has changed in the subject's medical history to warrant repeat treatment.

For subjects with completion of a full course of anti-TB therapy but insufficient documentation the investigator should consult with the AbbVie TA MD.

Newly initiated prophylactic treatment should be captured in the eCRF and in the source documents. Prior therapy should be captured in the eCRF.

During the study, subjects with new evidence of latent TB should initiate prophylactic treatment immediately per local guidelines and complete at least 6 months of prophylaxis. Study drug(s) should not be withheld and isoniazid should be initiated and 2 to 4 weeks later (per local guidelines), subject should be re-evaluated (unscheduled visit) for signs and symptoms of isoniazid toxicity.

If the subject is experiencing signs or symptoms suspicious for active TB or something has changed in the subject's medical history to warrant a repeat test, the case (including the TB test results) must be discussed with the AbbVie TA MD.

### **Chest X-Ray**

Chest x-ray (posterior-anterior view and lateral view) is required (in Japan and China, a computerized tomography [CT] scan of the chest may be performed in lieu of a chest x-ray, at the investigator's discretion) for all subjects at Screening to rule out the presence of TB or other clinically relevant findings.

The chest x-ray will not be required if the subject had a previous normal chest x-ray (posterior-anterior and lateral views) (or normal CT Scan of the chest) within 90 days of Screening, provided all source documentation is available at the site, as outlined below and provided nothing has changed in the subject's medical history to warrant a repeat test.

Subjects can have a repeat chest x-ray at any time during the study as warranted based on the opinion of the investigator.

A radiologist or pulmonologist must perform an assessment of the chest x-ray (or CT scan of the chest for subjects in Japan and China). The principal investigator will indicate the clinical significance of any findings and will sign and date the report. In the assessment of the chest x-ray (or CT scan of the chest for subjects in Japan and China) the principal investigator or their designee must indicate the presence or absence of (1) calcified granulomas, (2) pleural scarring/thickening, and (3) signs of active TB. If the chest x-ray demonstrates changes suggestive of previous TB (e.g., calcified nodule, fibrotic scar, apical or basilar pleural thickening) or other findings that are clinically significant, the principal investigator should contact the AbbVie TA MD before enrolling the subject.

### **12-Lead Electrocardiogram (ECG)**

For all subjects, a resting 12-lead ECG will be performed as specified in [Appendix C](#). A qualified physician will interpret the clinical significance of any abnormal finding, sign, and date each ECG. ECGs with QT interval corrected for heart rate using Fridericia's correction formula (QTcF) should be reported (or calculated) and documented in the source documents and later transcribed on to the appropriate eCRF if QTcF prolongation is observed. A valid QTcF cannot be calculated in subjects who have a pacemaker or supraventricular or ventricular conduction abnormalities. In cases of QTcF prolongation, the baseline QTcF will need to be entered into the appropriate eCRF for comparison as well. In addition, any clinically significant findings will be documented in the source documents and later transcribed on to the appropriate eCRF. Each signed original ECG will be monitored by the responsible site monitor and kept with subject's source documents onsite.

For subjects with a normal ECG taken within 90 days of Screening, a repeat ECG at Screening will not be required, provided source documentation is available and provided nothing has changed in the subject's medical history to warrant a repeat ECG. If there are

other findings that are clinically significant, the investigator must contact the AbbVie TA MD before enrolling the subject.

Subjects can have a repeat ECG at any time during the study as warranted based on the opinion of the investigator.

At Week 12 or Week 24, in the event this may not be performed due to the COVID-19 or any pandemic, the site should perform the 12-lead ECG at the next earliest feasible visit or arrange to have an alternative acceptable local facility perform the ECG.

### **Height and Weight**

Height will be measured at the Screening Visit only (with shoes off). Body weight will be measured at all scheduled visits, as specified in [Appendix C](#). All measurements will be recorded in metric units where applicable.

### **Vital Signs**

Vital sign determinations of systolic and diastolic BP in sitting position, pulse rate, respiratory rate, and body temperature will be obtained at visits specified in [Appendix C](#). Blood pressure, pulse rate, body temperature, and respiratory rate should be performed before blood draws are performed.

### **Physical Examination**

A complete physical examination will be performed at Screening, Baseline, Week 12, and Week 24/PD as specified in [Appendix C](#) and must include an assessment of EIMs and fistulas. The physical examination at the Baseline Visit will serve as the baseline physical examination for the entire study. Physical examinations at all other visits (including unscheduled visits) are symptom based and should include the assessment of EIMs, and presence or absence of fistulas as part of calculating the CDAI. The presence or absence of (1) arthritis/arthralgia, (2) iritis/uveitis, and (3) erythema nodosum, pyoderma gangrenosum, and aphthous stomatitis will be collected for the assessment of EIMs.

At Baseline, Week 12, and Week 24/PD, the number of fissures, draining and non-draining enterocutaneous (perianal and abdominal) and rectovaginal fistulas should be recorded, including the number of fistulas draining upon gentle compression. Enterocutaneous fistulas will be considered draining when there is drainage upon gentle compression, and rectovaginal fistulas will be considered draining based on either presence of drainage on physical examination or presence of relevant symptoms (e.g., passage of rectal material or flatus from the vagina). A complete examination of the presence and number of draining and non-draining fistulas during Screening or during the visit for endoscopy at Screening, Week 12, or Week 24/PD may be used for the Baseline, Week 12, or Week 24/PD visits, respectively, and does not need to be repeated at the respective visit.

Physical examination abnormalities noted by the investigator at Baseline prior to the first dose of study drug will be recorded in the subject's medical history; abnormalities noted after the first dose of study drug will be evaluated and documented by the investigator as to whether or not the abnormality is an AE (see Section 6.1.1.1 for AE definition). All findings, whether related to an AE or part of each subject's medical history, will be captured on the appropriate eCRF page.

At any time, a symptom-directed physical examination can be performed as deemed necessary by the investigator.

